4.1.8 Withdrawal of Informed Consent for Data and Biological Samples

Biological Samples Obtained for the Main Study

Study data are protected by the use of a SID number, which is a number specific to the subject. The investigator is in control of the information that is needed to connect a study sample to a subject. A subject may withdraw consent at any time by notifying the investigator. If consent is withdrawn, any data or samples collected prior to that time may still be given to and used by the sponsor but no new data or samples will be collected unless specifically required to monitor safety of the subject.

Samples Obtained for Future Research

Samples obtained for future research will be labeled with a sample identification number but will not be labeled with personal identifiers such as the subject's name. A file linking this sample identification number with the SID number will be kept in a secure place at the sponsor with restricted access. If the subject withdraws consent for participating in the future research, this link will allow the sponsor to locate the subject's sample and destroy it. The coding of samples and results is to ensure that these research results are kept confidential by keeping the subject's identity and these results separate.

If the subject consents to have his/her samples used for future research, this additional research may not start immediately and may start at any time during the storage period. The subject's sample(s) will be stored by the sponsor with similar samples from other subjects at a secure central laboratory. The subject's samples will not be kept for more than 25 years after the end of the study in which they were collected. If the subject chooses not to allow his/her study samples to be used for future research, the samples will be destroyed by the sponsor once they are no longer required for the main study.

If consent is withdrawn after a sample has been taken but before the subject's sample is sent to the sponsor for future research, the investigator will arrange to have it destroyed. If consent is withdrawn after the subject's sample(s) have been sent to the sponsor for future research, the sponsor and the investigator will ensure that these sample(s) are destroyed unless the sample identification number has been removed and the subject can no longer be linked to any sample(s). However, if the subject's sample(s) have already been used for research, the sponsor is not required to destroy results of this research. In this case only the remaining sample(s) will be destroyed.

4.2 Schedule of Study Procedures

All subjects who are assigned a SID number and receive any investigational product will be followed according to the protocol unless consent is withdrawn. The investigator must notify the sponsor or designee of deviations from protocol visits or evaluations and these evaluations, if applicable, must be rescheduled or performed at the nearest possible time to the original schedule. Protocol deviations will be recorded on the source document with an explanation for the deviation and on logs designated for capturing protocol deviations. The investigator must comply with the applicable requirements related to the reporting of protocol deviations to the Institutional Review Board (IRB)/Independent Ethics Committee (IEC).

4.2.1 Enrollment/Screening Period

[Table 4.2.1-1](#) shows all procedures to be conducted at the screening visit. Assessments should be performed in the order shown in the table except that vital signs, height, and weight may be performed at any point in the history and physical examination. Urinalysis may be performed at any time after informed consent has been obtained.

Whenever vital signs, 12-lead ECGs, and blood draws are scheduled for the same nominal time, phlebotomy should occur after the vital signs and ECG have been completed.

A subject who is to be rescreened will be considered a screening failure and, after providing informed consent a second time, will be rescreened, including all Visit 1 (Day -30 to Day -1) assessments. Subjects who are screening failures based on abnormalities of laboratory values or ECG abnormality may not be rescreened.

Table 4.2.1-1 Schedule of Screening Procedures

Study Period	Screening
Visit No.	V1
Procedure / Study Day	Day -30 to Day -1
Written informed consent/assignment of SID number	X
Medical history including concomitant medications and assessment of AEs and SAEs	X
Physical examination, weight, height, vital signs	X
ECG	X
Blood for chemistry, hematology, and coagulation parameters	X
Urinalysis	X
Verify eligibility criteria	X

AE = adverse event; ECG = electrocardiogram; SAE = serious adverse event; SID = subject identification; V = visit

Description of Study Procedures, Screening, Visit 1

All screening procedures must be performed within 30 days before randomization (Day -30 to Day -1). The screening evaluations may be carried out over more than one visit. Written informed consent and any locally required privacy act document authorization must be obtained prior to performing any protocol-specific procedures, including screening evaluations. However, if evaluations that have been performed for other purposes prior to informed consent are otherwise suitable for use as screening evaluations, they need not be repeated if the subjects allow use.

1. Obtain written informed consent and appropriate privacy act document authorization
2. Assign a SID number
3. Perform medical history
4. Perform physical examination, including height, weight, and vital signs
5. Perform an ECG (may be performed before or after physical examination)
6. Collect blood for screening samples, including serum chemistry, hematology and coagulation parameters
7. Collect urine for urinalysis
8. Assess AEs, SAEs

9. Record concomitant medications
10. Verify eligibility criteria

4.2.2 Randomized Treatment and Follow-up Periods

All randomized subjects will be followed for 360 days for safety and for vaccine immunogenicity. Subjects who plan to withdraw consent and who are willing to come to the study site should have study procedures for Day 361 performed unless blood for immunogenicity has been obtained within the previous 2 weeks. All subjects should have medical histories updated at the time of last contact to obtain the maximal duration of safety follow-up.

Subjects will be considered lost to follow-up only if no contact has been established by Day 361 + 10 days, such that there is insufficient information to ascertain the subject's status at that time. Subjects refusing to return to the site or to continue participation in the study should be documented as "withdrawal of consent" rather than "lost to follow-up."

Investigators should document attempts to re-establish contact with missing subjects until Day 361 + 10 days. If contact with a missing subject is re-established, the subject should not be considered lost to follow-up and any evaluations should resume according to the protocol.

[Table 4.2.2-1](#) shows all procedures to be conducted during the randomized treatment and follow-up periods. Assessments on Day 1 should be performed in the order shown in the table, except that vital signs may be performed at any time prior to verification of eligibility criteria. For each phlebotomy, blood samples may be obtained in any order. Urinalysis may be performed at any time after randomization and before dosing.

Table 4.2.2-1 Schedule of Treatment and Follow-up Periods Study Procedures

Study Period	Treatment Period	Follow-up Period														
		V2	T3	V4	T5	V6	V7	V8	T9	T10	V11	T12	T13	V14	T15	T16
Visit (V) /Telephone Contact (T) No.	V2	T3	V4	T5	V6	V7	V8	T9	T10	V11	T12	T13	V14	T15	T16	V17
Procedure/Study Day	D1	D3 +3	D8 +3	D14 +4	D 29 +4	D 61 ±5	D 91 ±5	D 121 ±12	D 151 ±12	D 181 ±12	D 211 ±12	D 241 ±12	D 271 ±12	D 301 ±12	D 331 ±12	D 361 ±10
Medical history ^a	X	X	X	X	X	X	X	X	X	X	X	X	X	X	X	X
Physical examination (weight required D1 only)	X		X ^b		X ^b	X ^b	X ^b			X ^b			X ^b			X ^b
Vital signs	X ^c															
Verify eligibility criteria	X ^d															
Randomization	X															
Serum chemistry, hematology, and urinalysis ^e	X ^d		X		X											
Serum storage at baseline for potential later use for safety assessment	X ^d															
Humoral immunogenicity serum sample	X ^d				X	X	X			X			X			X
Cell-mediated immunity PBMC (whole blood) sample	X ^d		X		X											
Investigational product administration followed by 30 minutes of observation with vital signs prior to discharge	X															
Provide thermometers, tape measures and diary cards ^f	X															

Table 4.2.2-1 Schedule of Treatment and Follow-up Periods Study Procedures

Study Period	Treatment Period	Follow-up Period														
		V2	T3	V4	T5	V6	V7	V8	T9	T10	V11	T12	T13	V14	T15	T16
Visit (V) /Telephone Contact (T) No.	V2	T3	V4	T5	V6	V7	V8	T9	T10	V11	T12	T13	V14	T15	T16	V17
Procedure/Study Day	D1	D3 +3	D8 +3	D14 +4	D 29 +4	D 61 ±5	D 91 ±5	D 121 ±12	D 151 ±12	D 181 ±12	D 211 ±12	D 241 ±12	D 271 ±12	D 301 ±12	D 331 ±12	D 361+10
Assessment of solicited symptoms	X	X	X													
Assessment of AEs	X	X	X	X	X											
Assessment of SAEs, NOCDs, AESIs	X	X	X	X	X	X	X	X	X	X	X	X	X	X	X	X
All concomitant medications or prohibited concomitant medications only	X ^g	X ^g	X ^g	X ^g	X ^g	X ^h	X ^h	X ^h	X ^h	X ^h	X ^h	X ^h	X ^h	X ^h	X ^h	X ^h

AE = adverse event; AESI = adverse event of special interest; D = Day; NOCD = new onset chronic disease; PBMC = peripheral blood mononuclear cells; SAE = serious adverse event; V = subject visit; T = telephone follow-up

- ^a Update history for interim events or clarification or update (targeted) physical examination of areas suggested by medical history. Additional laboratory tests may be performed as clinically indicated, and abnormal laboratory values must be repeated for confirmation
- ^b Targeted physical examination, if appropriate
- ^c Prior to and 20 to 30 minutes after dosing
- ^d Prior to dosing
- ^e A baseline serum sample will be retained for all subjects to be used if an AESI occurs for which a baseline marker might help to clarify the temporal relationship to vaccination. Samples left over from the clinical laboratory testing at other timepoints will also be retained to assess safety events that might theoretically be related to an adjuvanted vaccine.
- ^f After providing first set, only provide thermometers and tape measures if replacement needed
- ^g All concomitant medications. On the dosing visit (V2), concomitant medications should be assessed prior to dosing to include in assessment of eligibility.
- ^h Prohibited concomitant medications only (Section 4.7.2)

4.2.2.1 Description of Study Procedures, Treatment Period

Day 1: Dosing (Visit, V2)

1. Update medical history, including concomitant medications
2. Perform physical examination to update since screening, including weight
3. Collect vital signs
4. Verify eligibility criteria
5. Randomize and assign product kit number
6. Collect urine for urinalysis (may be collected after phlebotomy)
7. Collect blood samples (see Laboratory Manual for details):
 - for serum chemistry and hematology
 - for potential use in assessing treatment-emergent safety events
 - for humoral immunogenicity assays
 - for cell-mediated immunogenicity assays
8. Administer investigational product and observe for at least 30 minutes. Vital signs must be repeated between 20 and 30 minutes post dose.
9. Provide thermometers, diary cards, tape measures, and instructions for completing diary cards; ensure subject understands how to measure local reactions and take temperature
10. Assess for all solicited symptoms, and treatment-emergent AEs, SAEs, NOCDs, and AESIs
11. Record all concomitant medications

4.2.2.2 Description of Study Procedures, Follow-up

A description of each follow-up study visit and telephone contact is provided below.

Day 3 + 3 (Telephone Contact, T3)

1. Update medical history
2. Assess for all solicited symptoms, and treatment-emergent AEs, SAEs, NOCDs, and AESIs
3. Update all concomitant medications

Day 8 + 3 (Visit, V4)

1. Update medical history, perform targeted physical examination if appropriate
2. Assess for all solicited symptoms, AEs, SAEs, and treatment-emergent NOCDs and AESIs
3. Update all concomitant medications
4. Collect urine for urinalysis (may be collected after phlebotomy)
5. Collect blood samples:

- for serum chemistry and hematology
- for cell-mediated immunogenicity assays

Day 14 + 4 (Telephone Contact, T5)

1. Update medical history
2. Assess for all treatment-emergent AEs, SAEs, NOCDs, and AESIs
3. Update all concomitant medications

Day 29 + 4 (Visit, V6)

1. Update medical history, perform targeted physical examination if appropriate
2. Assess for all treatment-emergent AEs, SAEs, NOCDs, and AESIs
3. Update all concomitant medications
4. Collect urine for urinalysis (may be collected after phlebotomy)
5. Collect blood samples:
 - for serum chemistry and hematology
 - for humoral immunogenicity assays
 - for cell-mediated immunogenicity assay

Day 61 ± 5 (Visit, V7)

1. Update medical history, perform targeted physical examination if appropriate
2. Assess for all treatment-emergent SAEs, NOCDs, and AESIs
3. Assess prohibited concomitant medications
4. Collect serum sample for humoral immunogenicity assays

Day 91 ± 5 (Visit, V8)

1. Update medical history, perform targeted physical examination if appropriate
2. Assess for all treatment-emergent SAEs, NOCDs, and AESIs
3. Assess prohibited concomitant medications
4. Collect serum sample for humoral immunogenicity assays

Day 121 ± 12 (Telephone Contact, T9)

1. Update medical history
2. Assess for all treatment-emergent SAEs, NOCDs, and AESIs
3. Assess prohibited concomitant medications

Day 151 ± 12 (Telephone Contact, T10)

1. Update medical history
2. Assess for all treatment-emergent SAEs, NOCDs, and AESIs
3. Assess prohibited concomitant medications

Day 181 ± 12 (Visit, V11)

1. Update medical history, perform targeted physical examination if appropriate
2. Assess for all treatment-emergent SAEs, NOCDs, and AESIs
3. Assess prohibited concomitant medications
4. Collect serum sample for humoral immunogenicity assays

Day 211 ± 12 (Telephone Contact, T12)

1. Update medical history
2. Assess for all treatment-emergent SAEs, NOCDs, and AESIs
3. Assess prohibited concomitant medications

Day 241 ± 12 (Telephone Contact, T13)

1. Update medical history
2. Assess for all treatment-emergent SAEs, NOCDs, and AESIs
3. Assess prohibited concomitant medications

Day 271 ± 12 (Visit, V14)

1. Update medical history, perform targeted physical examination if appropriate
2. Assess for all treatment-emergent SAEs, NOCDs, and AESIs
3. Assess prohibited concomitant medications
4. Collect serum sample for humoral immunogenicity assays

Day 301 ± 12 (Telephone Contact, T15)

1. Update medical history
2. Assess for all treatment-emergent SAEs, NOCDs, and AESIs
3. Assess prohibited concomitant medications

Day 331 ± 12 (Telephone Contact, T16)

1. Update medical history
2. Assess for all treatment-emergent SAEs, NOCDs, and AESIs
3. Assess prohibited concomitant medications

Day 361 + 10 (Visit, V17)

1. Update medical history, perform targeted physical examination if appropriate
2. Assess for all treatment-emergent SAEs, NOCDs, and AESIs
3. Assess prohibited concomitant medications
4. Collect serum sample for humoral immunogenicity assays

4.3 Description of Study Procedures

4.3.1 Efficacy

This is a Phase 1a safety and immunogenicity study in healthy subjects, therefore disease evaluation is not planned.

4.3.2 Medical History and Physical Examination, Electrocardiogram, Weight, and Vital Signs

A complete medical history will be performed at screening and will be updated (targeted physical examination) at each subsequent subject visit to ensure adherence to inclusion/exclusion criteria, to identify safety events, and to identify events or medications that could affect study outcomes. A physical examination, including vital signs, will be conducted at screening (pelvic and rectal examinations are not required) and height and weight will be obtained. Physical examination, including weight and vital signs, will be updated on the day of dosing prior to administration of study vaccine.

At each study visit, targeted physical examinations will be performed if any AEs have occurred that would warrant an examination (for example, lung examination in the case of bronchitis; skin examination in the case of a rash, etc). Vital signs, height, and weight do not need to be performed except as needed for the assessment of an AE. A licensed, independent healthcare provider must perform the physical examinations in accordance with state licensing regulations. Height will be obtained at screening only.

Vital signs (temperature, blood pressure, pulse rate, and respiratory rate) will be obtained at screening and on the day of dosing prior to and at 20 to 30 minutes post dose. Temperature

may be collected by any route ([Marcy et al, 2004](#)). Abnormal vital signs must be repeated after the subject has been at rest for at least 5 minutes.

An ECG will be obtained at the screening visit with the subject supine.

4.3.3 Clinical Laboratory Tests

A Laboratory Manual will be provided to the sites that specifies the procedures for collection, processing, storage, and shipment of samples, as well as laboratory contact information, specific to this clinical research study.

Clinical laboratory safety tests will be performed in a licensed central clinical laboratory. Clinically significant abnormal laboratory results should be repeated as soon as possible (preferably within 24 to 72 hours).

The following clinical laboratory tests will be performed (see [Table 4.2.1-1](#) and [Table 4.2.2-1](#) for the schedules of tests):

Serum Chemistry

- Calcium
- Chloride
- Potassium
- Sodium
- Bicarbonate
- Aspartate transaminase (AST)
- Alanine transaminase (ALT)
- Alkaline phosphatase (ALP)
- Total and direct bilirubin
- Gamma glutamyl transferase (GGT)
- Creatinine
- Blood urea nitrogen (BUN)
- Glucose
- Albumin
- Total protein

Note for serum chemistries: Tests for AST, ALT, ALP, and total and direct bilirubin must be conducted concurrently and assessed concurrently.

Hematology

- White blood cell (WBC) count with differential
- Hematocrit
- Hemoglobin
- Platelet count

Urinalysis

- Color
- Appearance
- Microscopy including WBC/high power field (HPF), red blood cell (RBC)/HPF
- Specific gravity
- pH
- Dipstick assessment*

*Dipstick assessment must include at least glucose, blood, and protein; other parameters may be included depending on the characteristics of the dipstick being used

Other Safety Tests

- Coagulation tests: prothrombin time (PT), partial thromboplastin time (PTT) at screen only

A baseline serum sample will be retained for all subjects to be used if an AESI occurs for which a baseline marker might help to clarify the temporal relationship to vaccination. Samples left over from clinical laboratory testing at other timepoints will also be retained to assess safety events that might theoretically be related to an adjuvanted vaccine.

4.3.4 Immunogenicity Evaluation and Methods

Samples for immunogenicity testing will be obtained and handled in accordance with the Laboratory Manual provided separately.

4.3.4.1 Humoral Immunity

Humoral immunity against RSV will be assessed by:

- RSV A microneutralization assay
- Anti-F IgG assay (derived from RSV-specific 4-plex MSD assay)

Humoral immunity to detect wild-type RSV infection will be assessed by RSV anti-Ga, anti-Gb or anti-N antibodies (derived from RSV-specific 4-plex MSD assay).

4.3.4.2 Cell-mediated Immunity

Cell-mediated immunity will be assessed using an IFN γ ELISPOT assay to measure T-cell responses to the RSV F peptide pool using thawed, cryopreserved peripheral blood mononuclear cell (PBMC) samples ([Patton et al, submitted](#)).

4.3.5 Estimate of Volume of Blood to Be Collected

The amount of blood to be taken from an individual subject is estimated on a per-day basis across all tests combined and totaled for the study in [Table 4.3.5-1](#). Additional samples may be obtained for assessment of safety; for example, clinically significant abnormal laboratory values are to be repeated, preferably within 24 to 72 hours, and certain AESIs for an adjuvanted vaccine may require serologic assessment such as antinuclear antibody, rheumatoid factor, etc. The baseline stored sample for safety will be used to assess such serologies if warranted by a clinical event. The maximum total volume of blood that will not be exceeded in the study for a given subject is approximately 224 mL per 6-week period (unless additional laboratory tests are performed for medical management).

Table 4.3.5-1 Estimated Blood Volume to be Collected by Visit

Visit Day	Visit Number	Estimated Blood Volume (mL)
Day -30 to Day -1	1	8.2
Day 1	2	67
Day 8	4	55.5
Day 29	6	65.5
Day 61	7	10
Day 91	8	10
Day 181	11	10
Day 271	14	10
Day 361	17	10
Total		246.20

4.4 Study Suspension or Termination

The Sponsor reserves the right to temporarily suspend or terminate this study at any time. The reasons for temporarily suspending or terminating the study may include but are not limited to the following:

1. The incidence or severity of AEs in this or other studies indicates a potential health hazard to subjects. See Section 4.4.1 for specific study-stopping criteria
2. Subject enrollment is unsatisfactory
3. Noncompliance that might significantly jeopardize the validity or integrity of the study

If MedImmune determines that temporary suspension or termination of the study is required, MedImmune will discuss the reasons for taking such action with all participating investigators (or head of the medical institution, where applicable). When feasible, MedImmune will provide advanced notice to all participating investigators (or head of the medical institution, where applicable) of the impending action.

4.4.1 Enrollment and Dosing Stopping Criteria

If any of the following events occur, administration of investigational product will be stopped and no additional subjects will be randomized into the study until review by the ESMC.

Events that meet enrolling and dosing stopping criteria 1 through 4 must be reported within 24 hours of knowledge of the event to MedImmune Patient Safety using the Safety Fax Notification Form (see Section 5.6 for contact information). The occurrence of these events does not automatically make an AE serious but, if the consequences of the event are serious, for example, death or hospitalization, the event is serious and must be reported as an SAE (see Section 5.2). These events may or may not be considered to be serious (ie, may or may

not meet criteria for SAEs as described in Section 5.2). Events that might meet enrollment and dosing stopping criteria 5 and 6, particularly investigational product-related Grade 3 or Grade 4 AEs, must first be conveyed to the site monitor and then be entered into the electronic case report form (eCRF) within 24 hours of awareness of the event to trigger reporting to the medical monitor.

1. Death in any subject in which the cause of death is assessed as related to investigational product
2. Anaphylactic reaction related to investigational product in any subject
3. Adverse event of special interest for an adjuvanted vaccine other than new onset or exacerbation of thyroid disorders occurring in any subject enrolled in a cohort dosing with MEDI7510 (RSV sF cohorts may continue dosing and enrolling if this stopping criterion is met)
4. Any SAE assessed as related to investigational product, or any SAE that is not clearly and obviously unrelated to investigational product
5. Any single Grade 4 AE assessed as related to investigational product occurring in any cohort or any two Grade 3 AEs of the same type assessed as related to investigational product occurring in more than one subject in any single cohort
6. Any other safety finding assessed as related to investigational product that, in the opinion of the investigators, the sponsor, or the ESMC might contraindicate further dosing of study subjects

If any of the above-listed events occurs, investigators will be notified immediately. The US Food and Drug Administration (FDA) will be promptly notified, and IRBs/IECs should be notified by investigators in accordance with their IRB/IEC's requirements. The ESMC will perform a prompt cumulative review of safety data and the circumstances of the event in question in order to make a recommendation to MedImmune regarding continued dosing. MedImmune will review the ESMC recommendation and the events to decide on a course of action. This review will be shared with the US FDA and investigators, who should submit to their IRB/IEC in accordance with its requirements. If the AE is considered potentially dose limiting but permits continued assessment, another 12 subjects may be enrolled in the same dose cohort. If the AE is considered dose limiting for the current dose cohort, another 12 subjects may be enrolled in the next lower MEDI7510 dosing cohort.

Any subjects who have already received investigational product and are currently in the study at the time dosing-stopping criteria are met will continue to be followed by the investigator for safety.

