3.1.2 Treatment Regimen

A total of 144 subjects is planned to be randomized at a 5:1 ratio in 6 cohorts to receive a single dose of either RSV sF or placebo or MEDI7510 or placebo administered by IM injection on Day 1 as described in [Table 3.1.2-1](#).

Table 3.1.2-1 Treatment Regimen

Cohort	Number of Subjects	Treatment Regimen
1	24	20 µg RSV sF (N = 20) or placebo (N = 4) as a single IM dose
1a	24	20 µg MEDI7510 (N = 20) or placebo (N = 4) as a single IM dose
2	24	50 µg RSV sF (N = 20) or placebo (N = 4) as a single IM dose
2a	24	50 µg MEDI7510 (N = 20) or placebo (N = 4) as a single IM dose
3	24	80 µg RSV sF (N = 20) or placebo (N = 4) as a single IM dose
3a	24	80 µg MEDI7510 (N = 20) or placebo (N = 4) as a single IM dose

GLA = glucopyranosyl lipid A; IM = intramuscular; RSV sF = respiratory syncytial virus soluble fusion antigen; SE = squalene emulsion; w/v = weight per volume

Note: MEDI7510 comprises RSV sF with 2.5 µg GLA + 2% (w/v) SE; placebo = normal saline

Staggering of Dosing

Within individual cohorts, dosing will be staggered for safety. A minimum of 3 days is required between the initial (N = 5) and final (N = 19) dosing groups of subjects within each cohort.

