3.1.3 Cohort Escalation

A partially parallel cohort progression design will be used for this study, with collection, compilation, and assessment by the External Safety Monitoring Committee (ESMC) of a total of 7 days of safety and laboratory data from the preceding single or concurrent cohorts required prior to enrolling in the subsequent cohort(s). In this schema, Cohort 1 will be enrolled first and all subjects in Cohort 1 will be followed for safety for 7 days prior to enrollment in any subsequent cohort(s). Cohort progression will occur after review of all cumulative safety data, including safety laboratory data (but not including immunogenicity data) by the MedImmune medical monitor, who will review only blinded data, and the ESMC, who will review blinded data and can choose to also review unblinded data. The principal investigators are invited to the open session for blinded review of data. External Safety Monitoring Committee review of cohort progression is described in [Section 4.8.5](#). If there are no safety concerns, Cohorts 1a and 2 may enroll at the same time. After all subjects in those cohorts have been followed for 7 days, Cohorts 2a and 3 will be enrolled in the same

fashion. After all subjects in Cohorts 2a and 3 have been followed for 7 days, Cohort 3a will be completed.

Cohort expansion will occur at the recommendation of the ESMC as described in Section 4.4.1. If cohort expansion occurs, a total of 12 subjects will be added to the expanded cohort with the same randomization ratio (5:1) applied.

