3.2 Study Design and Dose Rationale

The study will be randomized, placebo-controlled, and double-blind to ensure a robust design and minimize bias.

The sample size for this study is selected to support the assessment of the safety of MEDI7510.

Both antibody and cell-mediated immunity are considered to be important to the immune response in the target population of older adults, with the adjuvant expected to provide for the cell-mediated responses that would not be expected from RSV sF alone and also to contribute to the duration of antibody responses. Thus, after the initial safety of a dose of RSV sF has been assessed, that dose will be assessed in combination with a low dose of adjuvant. An antigen dosage that maximizes humoral and cell-mediated immune responses and that is safe and tolerable will be selected for further study.

Subjects will be followed for 360 days after dosing both to assess the long-term safety of the antigen and adjuvant combination and to permit assessment of the duration of the immune response.

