4.8.5 External Safety Monitoring Committee

A study-specific ESMC that is advisory to MedImmune will provide ongoing safety surveillance of the study, with regularly scheduled reviews of safety for cohort escalation decisions. This committee will also review data at other timepoints in response to events meeting enrollment and dosing stopping criteria (Section 4.4.1) or events assessed as medically relevant by the medical monitor or one of the site investigators. Details are provided in the ESMC charter.

For cohort escalation decisions, the ESMC and the MedImmune medical monitor will review blinded data by cohort, including all AEs/SAEs, laboratory parameters, and AESIs observed between dosing of the initial subject in the cohort(s) and the time that the final subject enrolled in the cohort(s) has completed 7 days of safety follow-up. Cumulative safety data

for other cohorts will also be reviewed. In addition, the ESMC has the option of reviewing unblinded data but cannot reveal any grouped or unblinded data to blinded MedImmune or site staff. Dose escalation decisions and outcomes of reviews of safety and other relevant data will be communicated to MedImmune. The sponsor will notify sites when enrollment into each dose cohort has been completed and when enrollment into the next dose cohort is permitted. The US FDA and IRBs/IECs will be notified when the ESMC has recommended that study dosing be halted or that cohort escalation should not occur.

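### The step-down rule in Section 4.4.1 names only a MEDI7510 cohort, so a dose-limiting AE on antigen alone in Cohort 2 or 3 leads to an adjuvanted cohort and not to the matched lower RSV sF cohort

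*Protocol*

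**What the plan says.** Section 4.4.1 lists six stopping criteria and then gives two expansion options. If the AE is potentially dose limiting but assessment can continue, 12 more subjects may enter the same cohort. If it is judged "dose limiting for the current dose cohort, another 12 subjects may be enrolled in the next lower MEDI7510 dosing cohort". Section 3.1.3 refers back to Section 4.4.1 for expansion and names no other target.

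The criteria are not confined to the adjuvanted cohorts. Criterion 5 covers "Any single Grade 4 AE assessed as related to investigational product occurring in any cohort", and criteria 1, 2, 4 and 6 carry no cohort limit. Only criterion 3 is specific to MEDI7510, and it says so: "RSV sF cohorts may continue dosing and enrolling if this stopping criterion is met".

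On sequence, Section 3.1.3 states that "Cohorts 1a and 2 may enroll at the same time" once Cohort 1 has been reviewed, and that Cohorts 2a and 3 follow in the same fashion. Under Section 4.8.5 the escalation review covers data up to "the time that the final subject enrolled in the cohort(s) has completed 7 days of safety follow-up". Section 3.2 gives the reasoning: "after the initial safety of a dose of RSV sF has been assessed, that dose will be assessed in combination" with adjuvant.

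**The concern.** The protocol treats RSV sF and MEDI7510 as separate products. The note to Table 3.1.2-1 defines MEDI7510 as the antigen with 2.5 µg GLA and 2% SE, and criterion 3 contrasts the two within Section 4.4.1 itself. The step-down target therefore cannot easily be read as shorthand for either product.

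Taken as written, a dose-limiting toxicity seen with antigen alone is answered by adding subjects to a cohort that receives an adjuvant the affected subjects did not have. Two things are at stake. The first is safety: the adjuvanted target is the cohort enrolling alongside the affected one, and its scheduled review may not yet have taken place. The second is interpretation: if the 12 added subjects react, the data cannot separate a persisting antigen effect at the lower dose from an effect of GLA-SE. The next lower RSV sF cohort changes only the dose.

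**Working it through.** **Inputs.** Cohort doses and sizes: Section 3.1.1 and Table 3.1.2-1. Stopping criteria and expansion rule: Section 4.4.1. Enrolment order: Section 3.1.3. Stagger: Section 3.1.2. Allocation 5:1: Sections 3.1.3 and 4.8.2.

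**The plan's own figure.** 6 × 24 = 144 planned, and 144 + 12 × 6 = 216 at most. This reproduces Section 4.8.2.

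**Reach of the criteria.** 6 − 1 = 5 of the six criteria apply to the RSV sF cohorts.

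**Where the rule leads.** Cohorts 1 and 1a have no lower dose, which leaves 6 − 2 = 4 cohorts. The number in parentheses is the enrolment step.

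| Affected cohort | Target as written | Same-product target |
|---|---|---|
| 2: 50 µg RSV sF (2) | 1a: 20 µg MEDI7510 (2, parallel) | 1: 20 µg RSV sF (1) |
| 3: 80 µg RSV sF (3) | 2a: 50 µg MEDI7510 (3, parallel) | 2: 50 µg RSV sF (2) |
| 2a: 50 µg MEDI7510 (3) | 1a (2) | 1a (2) |
| 3a: 80 µg MEDI7510 (4) | 2a (3) | 2a (3) |

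The two columns differ for Cohorts 2 and 3 only.

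**Change in exposure for those two.** Antigen: 50 − 20 = 30 µg lower, and 80 − 50 = 30 µg lower. GLA: 0 to 2.5 µg, with SE added.

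**Subjects per expansion.** 12 × 5/6 = 10 active and 12 × 1/6 = 2 placebo.

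**Timing of the scheduled review.** Within each cohort, "A minimum of 3 days is required between the initial (N = 5) and final (N = 19) dosing groups". The last subject therefore completes 7 days of follow-up no earlier than 3 + 7 = 10 days after the cohort's first dose. The escalation review of the pair cannot come sooner, so a dose-limiting AE in Cohort 2 or 3 may be judged while the scheduled review of 1a or 2a is still pending. If the AE is judged at or after that review, the timing issue disappears and only the change of product remains.

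**Status of the same-product targets.** Cohort 1 must be reviewed before Cohort 2 opens, and Cohorts 1a and 2 before Cohort 3 opens. The same-product target has thus had its 7-day review in 4 of 4 cases. As written, that is certain in 2 of 4.

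**The case against.** The strongest reply is that the protocol uses the 7-day review to gate escalation to the next cohort, not further enrolment in a cohort already open. Cohorts 1a and 2a may each dose all 24 subjects before their own review, with only the stagger in between. A pending review is thus the normal state of an open cohort. This stands. The 2-of-4 against 4-of-4 count shows which targets are better established; it does not show a breach of a protocol requirement.

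A reader might also infer that the rule adds subjects to a cohort nobody has reviewed. The documents do not support that. An event in an RSV sF cohort that meets a criterion halts dosing and randomization until the ESMC has made a prompt cumulative review, which includes the target's data to date. The ESMC then recommends, the sponsor decides, and expansion is permitted, not required. Only the scheduled 7-day review may be outstanding.

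A second tempting inference is that the rule reverses the order in Section 3.2. It does not. The 20 µg antigen dose was assessed alone in Cohort 1 before 1a opened, and 50 µg in Cohort 2 before 2a opened. That 1a is the first human use of MEDI7510 comes from the base design, not from this rule.

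It can also be said that more data at a lower MEDI7510 dose serve the trial's aim of choosing an antigen dose for use with adjuvant. That is fair, but Section 4.4.1 does not give it as the reason for the target.

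Finally, the sentence may have been meant for MEDI7510 cohorts only. In that case Cohorts 2 and 3 have no step-down rule although the stopping criteria cover them, and the sentence still needs correcting.

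**Conclusion.** Wrong as written, low severity. The step-down rule is misdirected for the RSV sF cohorts: in two of the four cohorts with a lower dose, it leads to a different, adjuvanted product and leaves out the matched cohort that has already been reviewed. At most 12 subjects, 10 of them active, are affected per expansion. The ESMC halt and review, the permissive wording and the prior antigen-alone assessment limit the safety consequence; the mismatch of product remains.

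This rests on the literal meaning of MEDI7510, which the protocol defines and uses consistently in this section. The ESMC charter is not shown and may add safeguards. The protocol gives no AE rate, so no probability of the situation is claimed.

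**What to change.** In Section 4.4.1, replace the phrase that names the target with: *the next lower dose cohort of the same product (2 to 1, 3 to 2, 2a to 1a, 3a to 2a); no step-down applies to Cohorts 1 and 1a.*

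If the sponsor prefers to keep a MEDI7510 target for Cohorts 2 and 3, add that the 12 extra subjects may be enrolled only after the target cohort's planned 24 subjects have completed 7 days and the ESMC has reviewed those data. Tying the condition to the planned 24 matters: a condition on subjects dosed so far would be met trivially if few or none had been dosed.

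The cost is one sentence in an amendment. Under the same-product rule there is no wait for the target's 7-day review, but after an AE in Cohort 2 or 3 the added subjects inform on antigen alone. Under the alternative there is a delay to complete enrolment of the target, follow its last subject for 7 days (up to 7 + 3 = 10 with the Day 8 visit window), compile the data and convene the ESMC. The maximum of 216 is unchanged if each cohort is expanded at most once, as the stated figure already assumes.
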